17. EXTENSION PART

The extension part will provide continued access to FLX475 combined with pembrolizumab to subjects who have previously participated in HM-CCRI-201 study and are ongoing from the treatment with clinical benefit.

The primary objective of the extension part mainly is to provide continued treatment with FLX475 combined with pembrolizumab without the previous study procedures that intended to collect data for further analysis (e.g. efficacy, safety, biomarker, etc.). Survival and post-therapy long-term follow-up will also be discontinued.

17.1. Study Population

A subject will be eligible for inclusion in the extension part only if all of the following criteria are met:

1. Provision of signed / dated informed consent for the extension part.
2. Currently participating in HM-CCRI-201 study and is receiving treatment with FLX475 in combination with pembrolizumab.
3. Continued ability to swallow tablets without difficulty and retain orally administered study treatment.
4. For female subjects of childbearing potential, must be willing to continue to follow contraceptive guidance during the treatment period and for at least 120 days after the last dose of study treatment (refer to Section 9.2.4.).
5. For male subjects, must agree to continue to use 2 adequate methods of contraception, one of which must be a barrier method, during the study period and 120 days after the final dose of study treatment.

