9.1.2.2. During Treatment

All images during treatment will be sent to central imaging for further analysis. The first imaging assessment during study treatment should be performed 6 weeks (± 7 days) from Cycle 1, Day 1.

Subsequent tumor imaging should be performed every 6 weeks (± 7 days) or more frequently if clinically indicated for the first year of treatment. After 1 year, subjects who continue to receive study treatment will have imaging performed every 9 weeks (± 7 days) for up to 1 additional year.

The timing of tumor imaging should follow calendar days and should not be adjusted for delays in cycle starts. Tumor imaging should continue to be performed until Progressive Disease (PD) is identified by the investigator (unless the investigator elects to continue treatment and follow iRECIST), the start of new anticancer therapy, withdrawal of consent, loss to follow-up, death, 2 years of study treatment, or termination of the study by the Sponsor, whichever occurs first.

Objective response should be confirmed by a repeat imaging assessment. Tumor imaging to confirm PR or CR should be performed at least 4 weeks after the first indication of a response is observed. Subjects will then return to regularly scheduled imaging, starting with the next scheduled imaging time point. Subjects who receive additional imaging for confirmation do not need to undergo the next scheduled tumor imaging if it is less than 4 weeks later; tumor imaging may resume at the subsequent scheduled imaging time point.

Per iRECIST, investigator-assessed Progressive Disease (PD) in the clinically stable subjects should be confirmed by the investigator 4 to 8 weeks after the first radiologic evidence of Progressive Disease (PD). A subject with unconfirmed Progressive Disease may continue to receive study treatment at the discretion of the investigator until progression is confirmed by the investigator, provided the subject has met the conditions detailed in Section 9.1.3. Subjects who have confirmatory imaging do not need to undergo the next scheduled tumor imaging assessment if it is less than 4 weeks later; tumor imaging may resume at the subsequent scheduled imaging time point, if clinically stable.

Subjects who have confirmed Progressive Disease (PD) by iRECIST, as assessed by the investigator, will discontinue study treatment. Exceptions are detailed in Section 9.1.3.

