17.2. Study Procedures / Assessments

The Schedule of Procedures / Assessments is presented in the following [Flow Chart A](#).

Study visits will occur on Day 1 (± 3 days) of every cycle of 21 days, End of Treatment (EOT) and 30 days ($+7$ days) after the last dose of study treatment (Safety follow-up visit). Treatment cycles will be counted continuously regardless of dose interruptions (assessments corresponding to each cycle should be performed regardless of study drug administration). Unscheduled visit can be arranged when necessary. When a subject is discontinued from the study treatment, EOT and Safety follow-up visit will be performed, however, survival and post-therapy long-term follow-up will not be performed.

Tumor imaging and disease assessments will be performed throughout the study in accordance with local clinical practice and the appropriate assessment criteria as determined by the investigator to decide continued study participation and treatment with FLX475 combined with pembrolizumab. Only subjects considered by the investigator to be experiencing clinical benefit may continue on study treatment. Subjects will continue to receive study treatment for a maximum of 35 cycles (approximately 2 years).

Safety assessments will be proceeded through routine physical examination, ECOG performance status, vital sign measurement, 12-Lead electrocardiograms, echocardiograms or multiple-gated acquisition scans (when clinically required), laboratory assessments, and monitoring of adverse events (including serious adverse events).

Flow Chart A: Schedule of Procedures/Assessments for the Extension Part

Study Period/Cycle	Treatment (Each cycle = 21 days)		End of Treatment (EOT) Visit ^b	Safety Follow-up ^c
	Scheduled Visit (Day 1 of every cycle)	Unscheduled Visit ^a		
Cycle day	1 (±3)	NA		30 (+7) days after the last dose
General Procedure				
Informed Consent ^d	X			
Concomitant Medication	X	(X)	X	X
Investigational Product Dispensing and Administration				
FLX475 In-clinic Administration ^e	X			
Pembrolizumab Administration ^e	X			
FLX475 Dispensing ^f	X			
Clinical Procedure/ Assessments				
Physical Examination ^g	X	(X)	X	
ECOG Performance status	X	(X)	X	
Vital Signs ^h	X	(X)	X	
Triuplicate 12-Lead ECGs ⁱ	X	(X)	X	X ^s
ECHO or MUGA ^j				
AE/SAE Assessment ^k	X	(X)	X	X
Diary Card Dispensed/Collected	X		X	
Drug Accountability	X		X	
Laboratory Assessments				
Serum Chemistry ^l	X	(X)	X	
Hematology ^m	X	(X)	X	
Coagulation Tests ⁿ	X	(X)	X	

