17.5.1.1. Timing of Tumor Imaging

There will no longer be periodical tumor imaging and disease assessment required in the extension part of the study.

Tumor imaging and disease assessment will only be performed throughout the study in accordance with local clinical practice and the appropriate assessment criteria as determined by the investigator to decide continued study participation and treatment with FLX475 combined with pembrolizumab. Tumor imaging and disease assessment will be performed per investigator's discretion until Progressive Disease (PD) is confirmed.

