17.7. Statistical Consideration and Evaluation

As the main purpose of the extension part is to provide continued treatment with FLX475 combined with pembrolizumab without the previous study procedures that intended to collect data for further analysis, only the limited analysis for the safety data will be performed

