### 12.1 Tumor Assessment

Best overall response is the best response recorded from the treatment start date until the earliest of disease progression or last evaluable tumor assessment before events such as start of new anticancer therapy, death, lost to follow-up, etc. Objective response rate (ORR) is defined as the proportion of subjects whose confirmed best overall response is either Complete Response (CR) or Partial Response (PR) according to RECIST version 1.1. Disease control rate (DCR) is defined as the proportion of subjects with confirmed best overall response of CR, PR or SD according to RECIST version 1.1.

The hierarchy used to determine best overall response is CR>PR>SD>PD. [REDACTED]

The progression date is the earliest date among all images of PD lesion. If a subject does not experience PD in one disease assessment, his/her non-PD date will be the latest date among all images of the disease assessment.

Overall best response categories (including: CR, PR, PD, SD), ORR and DCR will be summarized (categorical descriptive analysis), together with the two-sided exact (Clopper-Pearson) 95% confidence intervals.

Based on the cumulative data about ORR along with prior assumption at each stage, posterior probability of ORR  $\geq 15\%$  for cohort 1 and ORR  $\geq 30\%$  for cohort 2 would be computed to determine go/no-go decision of the next stage. This cumulative data analysis will be implemented only if at least one response is observed from stage 1 of each cohort.

According to iRECIST, Best Overall Response (iBOR) of complete response (CR/iCR), partial response (PR/iPR), stable disease (SD/iSD), Progressive disease (iPD) or unevaluable (iUE) will be derived. iORR, iDCR, iTTR, iDoR and iPFS will be analyzed in the same manner as used analyses in accordance with RECIST 1.1. iPD is defined as the time point of first iUPD without subsequent iSD, iPR or iCR before study treatment discontinuation.

For the sum of diameter in target lesion, percent change from baseline at each scheduled tumor assessment time-point and maximal tumor shrinkage from baseline during the study will be summarized.

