### 12.2 Time to Event Endpoints (TTR, DoR, PFS and OS)

The time to event endpoints, including time to response (TTR), duration of response (DoR), progression-free survival (PFS) and overall survival (OS) will be summarized descriptively and graphically by the Kaplan-Meier methodology, as described in Section 3.3.

TTR is defined as the time from the date of first administration of study treatment to first documented CR or PR. DoR is measured from the date of the first observation of tumor response (CR or PR, whichever occurs first) to the date of disease progression or death for the subject with an objective response. PFS is defined as the time from the date of first administration of study treatment to determination of tumor progression by RECIST version 1.1 or death due to any cause, whichever occurs first. OS is defined as the duration of time from the treatment start date to time to death from any cause. If subjects survive at the time of analysis, the subject will be censored at the last date of survival confirmed.

TTR, DoR, PFS, and OS will be calculated in days, as well as in months.

For the tumor-related time-to-event endpoints, subjects who have not experience any event (Progressive Disease (PD) or Death) at the time of analysis will be censored at the date of the last evaluable tumor assessment. However, if the subject progresses or dies after two or more consecutive missed assessments

or start of new anticancer therapy, the subject will be censored at the time of the last evaluable assessment prior to starting new anti-cancer therapy/missed assessments. If the subject has no evaluable baseline/post-baseline assessment, subject will be censored at the date of first administration of study treatment. In case of subjects entering the extension part, the data will be treated as censored at the date of the last evaluable tumor assessment on or before the first administration date in the extension part.

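### A subject can enter the extension with a CR or PR still unconfirmed, no confirmatory scan is then required, and the visible SAP text gives best overall response no extension cut

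*Protocol*

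**What the plan says.** **Entry to the extension.** Protocol 17.1 lists five criteria: consent, the study-status criterion "Currently participating in HM-CCRI-201 study and is receiving treatment with FLX475 in combination with pembrolizumab", ability to swallow tablets, and two on contraception. Sections 17 and 17.2 add that the subject should be deriving clinical benefit. None concerns confirmation of a response.

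**Imaging after entry.** Protocol 17.5.1.1 states: "There will no longer be periodical tumor imaging and disease assessment required in the extension part of the study". Scans are left to the investigator, and the scheduled-visit list in 17.3 ties them to suspected progression. Section 17 names the main-part sections that carry over, and 9.1.2.2 is not among them. That section holds the confirmation rule: "Tumor imaging to confirm PR or CR should be performed at least 4 weeks after the first indication of a response is observed". Footnote s of Table 1.2:1 gives 4 to 6 weeks.

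**Criteria for reading extension scans.** Sections 17.2 and 17.5.1.1 say assessment is "in accordance with local clinical practice and the appropriate assessment criteria as determined by the investigator". Section 17.5.1 and footnote r of Flow Chart A name RECIST 1.1.

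**Primary endpoint.** SAP 12.1 defines ORR as the "proportion of subjects whose confirmed best overall response is either Complete Response (CR) or Partial Response (PR) according to RECIST version 1.1". The window is: "Best overall response is the best response recorded from the treatment start date until the earliest of disease progression or last evaluable tumor assessment", the latter taken before an open-ended list of events that does not name extension entry.

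**Extension cut.** For tumor-related time-to-event endpoints, SAP 12.2 says that data of subjects entering the extension are "censored at the date of the last evaluable tumor assessment on or before the first administration date in the extension part". For the extension as a whole, Protocol 17.7 says "only the limited analysis for the safety data will be performed".

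**The concern.** A confirmed-response endpoint needs two scans. The plan lets a subject leave the scheduled imaging between the first and the second, and nothing afterwards secures the second. Extension entrants are by design those still benefiting, so any loss falls on likely responders and lowers ORR.

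The SAP also handles extension entry for one family of endpoints only. DoR and PFS have an explicit cut. Best overall response, ORR and DCR have none in the visible text. Two programmers working from that text could report different primary ORRs from the same data, and one of those ORRs would not match the DoR reported beside it.

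**Working it through.** **1. Follow a subject whose first PR is on the last main-part scan.** The subject meets 17.1 and transfers before the repeat scan.

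- *Extension scans excluded* (the direction of Protocol 17.7): the PR is never confirmed, and the subject is a non-responder in ORR.
- *Extension scans included* (the literal SAP 12.1 window): a discretionary extension scan may confirm the PR, and the subject counts in ORR. DoR starts at the first PR, and SAP 12.2 censors at the last evaluable scan on or before the first extension dose. These are the same scan, so the duration has no length.

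**2. Follow a subject whose PR is first seen in the extension.** If extension scans are included and the PR is confirmed, the subject counts in ORR. DoR starts after the date at which SAP 12.2 censors it, so the duration is negative.

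Only one cut-off shared by 12.1 and 12.2 avoids these mismatches.

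**3. Reproduce the plan's figures.** Protocol 11.1 and SAP 2.4 use a uniform prior, so the posterior is Beta(1+X, 1+N−X) and

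P(ORR ≥ p0 | X, N) = 1 − F(p0; 1+X, 1+N−X), where F is the Beta distribution function.

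- Cohort 1 example, X = 1+6 = 7, N = 30, p0 = 0.15: 1 − F(0.15; 8, 24) = 0.918 (stated 92%).
- Cohort 2 example, X = 1+7 = 8, N = 20, p0 = 0.30: 1 − F(0.30; 9, 13) = 0.852 (stated 85%).

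Both reproduce.

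**4. Move one responder to non-responder.**

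| Case | ORR | Clopper-Pearson 95% CI | Posterior |
|---|---|---|---|
| Cohort 1, 7/30 | 23.3% | 9.9 to 42.3% | 0.918 |
| Cohort 1, 6/30 | 20.0% | 7.7 to 38.6% | 0.827 |
| Cohort 2, 8/20 | 40.0% | 19.1 to 63.9% | 0.852 |
| Cohort 2, 7/20 | 35.0% | 15.4 to 59.2% | 0.723 |

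The change is 1/30 = 3.3 points and 1/20 = 5 points. The cohort 2 example falls below 80%; the cohort 1 example does not. Away from the examples, one subject also crosses 80% in cohort 1 at 6/30 to 5/30 (0.827 to 0.683). At maximum size it does so at 11/60 to 10/60 in cohort 1 (0.804 to 0.697) and at 11/30 to 10/30 in cohort 2 (0.808 to 0.688).

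**5. How many subjects?** Under exclusion, those at risk are subjects whose first CR or PR falls within roughly the 4 to 6 weeks before transfer. The documents give neither the extension start date nor the number of entrants, so no count follows.

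**The case against.** The strongest reply is that the documents largely settle the matter. Protocol 17.7 confines extension analysis to safety. Protocol 17 and SAP 2.1 both describe the extension as running without procedures meant to collect efficacy data. The event list in SAP 12.1 is open-ended and could be read to include extension entry. Once extension scans are out, an unconfirmed PR is a non-response, as in any confirmed-response ORR. This stands in part: exclusion is the better-supported reading, and it is not wrong in itself. But SAP 12 and 12.1 do not visibly carry the rule, although 12.2 does for its own endpoints. Exclusion is also the reading under which a responder is lost for lack of a scan the main part already calls for.

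The redaction in SAP 12.1 follows directly on the response hierarchy, and no text is visible under 12.3. A rule may sit there, so the point is limited to the visible text.

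Four stronger readings are tempting but unsupported:

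- *ORR would rest on criteria the investigator picks.* Sections 17.2 and 17.5.1.1 suggest it, but 17.5.1 and footnote r name RECIST 1.1. This is a contradiction to reconcile. Discretionary scans and investigator reading also exist in the main part.
- *No scan of any kind is required.* Section 17.5.1 keeps brain imaging after CR and for treated brain metastases.
- *Stage decisions would be altered.* Nothing shows the extension opening before a stage review.
- *A definite share of responders is lost.* If transfer were equally likely at any time over 52 to 104 weeks after first response, the share would run from 4/104 (3.8%) to 6/52 (11.5%). The documents support no such assumption, and responders who stop before the extension are not exposed.

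**Conclusion.** The gap is real and narrow. Protocol 17.1 permits transfer with an unconfirmed CR or PR, nothing afterwards requires confirmation, and the visible SAP text cuts the time-to-event endpoints at extension entry but not the response endpoints. Followed literally, the plan can drop a responder from the primary ORR or count one whose DoR is censored on or before its start.

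Probably few subjects are affected. Each moves ORR by 3.3 points at n=30 or 5 points at n=20. The effect is on the final, descriptive ORR; it reaches the 80% posterior rule only if transfer precedes a stage review. The posterior figures rest on the plan's uniform prior and on counting an unconfirmed response as a non-response in the Treated Set. The conclusion also assumes that the redacted text of SAP 12.1 contains no extension rule.

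**What to change.** 1. **Protocol 17.1.** Add that a subject with a CR or PR not yet confirmed transfers once the confirmatory RECIST 1.1 scan called for by 9.1.2.2 has been done. Cost: one sentence, and a few transfers some weeks later. The scan is already part of the main study, and both parts list the same study treatment.
2. **SAP 12.1.** State that best overall response, ORR, DCR and their iRECIST counterparts use only assessments on or before the first administration date in the extension, as in 12.2, and that a response unconfirmed at that cut is not a confirmed response. Add a sensitivity analysis of ORR that also accepts confirmation on extension scans read by RECIST 1.1. Cost: two sentences and one table. If the redacted text already contains the rule, only the sensitivity analysis is new.
3. **Protocol 17.** Reconcile 17.2 and 17.5.1.1 with 17.5.1 and footnote r of Flow Chart A on which criteria apply to extension scans. Cost: editorial.

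Item 2 can be made in the SAP alone and by itself removes the ambiguity in the primary endpoint. Item 1 is what keeps the responder from being lost.

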17.2. Study Procedures / Assessments

The Schedule of Procedures / Assessments is presented in the following [Flow Chart A](#).

Study visits will occur on Day 1 (± 3 days) of every cycle of 21 days, End of Treatment (EOT) and 30 days ($+7$ days) after the last dose of study treatment (Safety follow-up visit). Treatment cycles will be counted continuously regardless of dose interruptions (assessments corresponding to each cycle should be performed regardless of study drug administration). Unscheduled visit can be arranged when necessary. When a subject is discontinued from the study treatment, EOT and Safety follow-up visit will be performed, however, survival and post-therapy long-term follow-up will not be performed.

Tumor imaging and disease assessments will be performed throughout the study in accordance with local clinical practice and the appropriate assessment criteria as determined by the investigator to decide continued study participation and treatment with FLX475 combined with pembrolizumab. Only subjects considered by the investigator to be experiencing clinical benefit may continue on study treatment. Subjects will continue to receive study treatment for a maximum of 35 cycles (approximately 2 years).

Safety assessments will be proceeded through routine physical examination, ECOG performance status, vital sign measurement, 12-Lead electrocardiograms, echocardiograms or multiple-gated acquisition scans (when clinically required), laboratory assessments, and monitoring of adverse events (including serious adverse events).

Flow Chart A: Schedule of Procedures/Assessments for the Extension Part

Study Period/Cycle	Treatment (Each cycle = 21 days)		End of Treatment (EOT) Visit ^b	Safety Follow-up ^c
	Scheduled Visit (Day 1 of every cycle)	Unscheduled Visit ^a		
Cycle day	1 (±3)	NA		30 (+7) days after the last dose
General Procedure				
Informed Consent ^d	X			
Concomitant Medication	X	(X)	X	X
Investigational Product Dispensing and Administration				
FLX475 In-clinic Administration ^e	X			
Pembrolizumab Administration ^e	X			
FLX475 Dispensing ^f	X			
Clinical Procedure/ Assessments				
Physical Examination ^g	X	(X)	X	
ECOG Performance status	X	(X)	X	
Vital Signs ^h	X	(X)	X	
Triuplicate 12-Lead ECGs ⁱ	X	(X)	X	X ^s
ECHO or MUGA ^j				
AE/SAE Assessment ^k	X	(X)	X	X
Diary Card Dispensed/Collected	X		X	
Drug Accountability	X		X	
Laboratory Assessments				
Serum Chemistry ^l	X	(X)	X	
Hematology ^m	X	(X)	X	
Coagulation Tests ⁿ	X	(X)	X	
Thyroid Function Tests ^o	X	(X)	X	
Urinalysis ^p	X	(X)	X	
Pregnancy Test ^q	X	(X)	X	
Disease Assessments				
Tumor Imaging/Staging (CT/MRI Scan) ^r	Radiological and clinical response assessments will be performed per investigator's discretion until Progressive Disease (PD) is confirmed			
Response Assessment ^r				

Pre-dose assessment (e.g. ECGs) should be obtained at study visits even when study treatment is being held or not given. All time points of the assessments are based on FLX475 administration.

- a. Unscheduled visits can be arranged if necessary. Study procedures will be at the discretion of the investigator.
- b. All Early Discontinuation / End of Study Treatment (ED/EOT) assessments must be performed within 14 days following the subject's last administration of study treatment and prior to initiation of any other treatment, whichever comes first.
- c. Safety follow-up visit will be scheduled 30 days (+7 days) from the final dose of study treatment. Follow up contact via telephone with the subject could be allowed unless any assessment must be performed for resolution of treatment-related AE.
- d. Informed consent must be obtained before the subject undergoes any study-specific procedures (only at initial visit to continue on in the extension part).
- e. On days when a clinical visit, the dose of FLX475 will be administered in the clinic after the specified visit assessments and procedures are performed. In addition, the dose of FLX475 should be self-administered in the clinic on Day 1 of each cycle. After a new supply of drug has been dispensed for that cycle, a diary card will be provided to each subject for recording of all dose administration information for drug accountability purposes. Pembrolizumab will be administered at a dose of 200mg IV over 30 minutes on Day 1 of each cycle. Pembrolizumab infusion should occur at least 1 hour after the dose of FLX475 is administered in the clinic. (Treatment cycles will be counted continuously regardless of dose interruptions and assessments corresponding to each cycle should be performed regardless of study drug administration).
- f. Dispensing of 3-week supply of FLX475 to the subject with instruction for self-administration at home.
- g. Weight measurement should be performed on Day 1 of each cycle and at ED/EOT.
- h. Vital signs (blood pressure, pulse rate, respiratory rate, and body temperature) will be collected with the subject in a sitting position. Vital signs will be assessed pre-dose at Day 1 of each cycles and at ED/EOT.
- i. Triplicate ECGs with tracings approximately 2 minutes apart must be collected in digital format on designated calibrated ECG equipment after at least 10 minutes of quiet rest in supine position. Meals should not be served shortly before ECGs. Pre-dose ECGs assessment will be performed on Day 1 of each cycles, at ED/EOT and at Safety follow-up visit (30 days (+7 days) from the final dose of study treatment).
- j. Assessment may be performed if clinically required at investigator's discretion.
- k. All AEs must be recorded and followed through 30 days following cessation of study treatment (or 30 days after final dose if the subject initiates new anticancer therapy), or until resolution, whichever comes first. All SAEs must be reported after the consent form is signed through 90 days following cessation of study treatment, or 30 days after final dose if the subject initiates new anticancer therapy, whichever occurs first.

- I. Serum Chemistry: includes sodium, potassium, chloride, total protein, bicarbonate, albumin, calcium, magnesium, phosphorous, glucose, BUN, creatinine (or CrCl), uric acid, total bilirubin, ALP, LDH, AST, ALT, amylase and lipase. Pre-dose serum chemistry to be obtained at Day 1 of each cycles and at ED/EOT.
- m. Hematology: WBC, RBC, ANC, hemoglobin, hematocrit, MCV, MCH, platelets, and WBC differential. Blood sampling for hematology to be obtained pre-dose at Day 1 of each cycles and at ED/EOT.
- n. Coagulation Tests (PT, PTT or aPTT, and INR) should be performed pre-dose on day 1 of every cycle and at ED/EOT.
- o. Thyroid function tests should be performed pre-dose on Day 1 of every odd-numbered cycle during study treatment (e.g., Cycle 3, 5, etc.) and at ED/EOT. Thyroid panel should include (1) Triiodothyronine (T3) or Free Triiodothyronine (FT3), (2) Free Thyroxine (FT4), and (3) Thyroid Stimulating Hormone (TSH).
- p. Urinalysis will include specific gravity, pH, blood, protein, glucose, ketones and bilirubin (microscopic UA with WBC, RBC, epithelial cells, bacteria, casts and crystals, only if necessary).
- q. Pregnancy testing (urine or serum) will be performed on Day 1 of every odd-numbered cycles (e.g., Cycle 3, 5, etc.) and at ED/EOT.
- r. Response and progression will be evaluated in this study using the revised Response Evaluation Criteria in Solid Tumors (RECIST) guideline (version 1.1). Radiological and clinical response assessments will be performed at any time per investigator's discretion until objective disease progression is confirmed.
- s. Triplicate ECGs on Safety follow-up visit is to be performed only on subjects who have experienced QTc interval prolongation during the study.

